5.3 Instructions for Use and Administration of Investigational Product

The investigational product kit carton will be provided to each site and will include two individual plastic pump containers in one carton. Each carton will also contain 4 applicators. Each investigational plastic pump container will contain sufficient drug product for a 21-day treatment period.

Each carton will have a unique randomization number printed on the label and each of the two pump container labels will display the same unique randomization number.

Each subject will be randomized to receive BBI-4000 (sofpironium bromide) Gel 5%, or 10%, or 15%, or Vehicle to apply, once a day, to each axilla (1 pump per axillae) using the supplied applicators for 42 consecutive days.

Subjects will be instructed to apply the investigational product to each axilla with one full actuation of the pump for each dose application. Each actuation of the pump corresponds to approximately 0.56 grams (i.e., 0.67 mL) of investigational product.

The subject will apply all doses of investigational product at night, prior to going to bed with the supplied applicators. Subjects will apply their first dose of gel prior to bedtime the night of their Baseline Visit. The subject should be instructed to use their investigational product each night with the last application the night before attending the end of-treatment evaluation (i.e., Day 43 visit). Subjects should wash the applicator each night after dosing. Four applicators are provided in each kit to compensate for loss or damage during handling; it is not necessary to use all 4 applicators over the specified dosing interval.

Page 27 of 65

To ensure accurate dosing, the Study Staff will be instructed to prime the pump container before dispensing to the subject by pressing the pump for three (3) sequential actuations and to discard to waste any dispensed gel from these 3 priming actuations.

The weight of the pump container with the cap on will be recorded after priming and will then be dispensed to the subject. Container 1 of 2 will be primed/weighed and then dispensed at the Baseline Visit along with the 4 applicators, and Container 2 of 2 will be primed/weighed/dispensed at Day 22 (Visit 8). Container 1 of 2 will be returned by the patient and weighed at Day 22 (Visit 8) and Container 2 of 2 will be returned by the patient and weighed at the End of Treatment Visit.

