7.2.10 Visit 13 (Day 43 ± 2 , GSP6) / End of Treatment

The following activities will be conducted:

- Collect vital signs (blood pressure, heart rate, respiratory rate and temperature) after subject has been seated for at least 2 minutes.
- Review changes to the subject's health (adverse events) and usage of concomitant medications/treatments.
- Subject to complete HDSM-Ax assessment.
- Subject to complete HDSS assessment.

- Subject to complete the DLQI questionnaire.
- Perform local tolerability assessments.
- Perform a UPT if applicable (FOCBP only). If positive, the subject shall be Early Terminated.
- Collect samples for laboratory assessments (hematology, chemistry and urinalysis).
- Collect subject's study product container 2 of 2, weigh and record weight of container.
- Evaluate subject compliance:
 - Ask subjects if they applied the study product to the right and left axilla each evening as directed and confirm reason for any missed doses.
 - Verbally confirm application process.
- Perform GSP; gravimetric assessment must occur between 7:00 am-11:00 am.
- Confirm the subject has adequate supply of the sponsor-provided non-antiperspirant deodorant and resupply as needed.
- Schedule the subject to return for the next study visit.

7.2.11 Visit 14 (Day 57 ± 3) / 2 Week Follow-up / End of Study

The following activities will be conducted:

- Collect vital signs (blood pressure, heart rate, respiratory rate and temperature) after subject has been seated for at least 2 minutes.
- Review changes to the subject's health (adverse events) and usage of concomitant medications/treatments.
- Subject to complete HDSM-Ax assessment.
- Subject to complete HDSS assessment.
- Perform local tolerability assessments.
- Perform GSP; gravimetric assessment must occur between 7:00 am-11:00 am.
- Discharge subject from the study.

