6.2 Schedule of Assessments

Table 2 Time and Events Table

Visit	1	2	3	4	5	6	7	8	9	10	11	12	13	14
PROCEDURE	Screening			Rescreening	Baseline								End of Treatment	Follow-up
Gravimetric Timepoint		GSP 1	GSP 2	GSP 3							GSP 4	GSP 5	GSP 6	
Day (allowable window)	Up to 35 days prior to GSP1	Up to 14 days from GSP1 to GSP3			Day 1 (within 7 days of Rescreening)	Day 8 (± 2)	Day 15 (± 2)	Day 22 (± 2)	Day 29 (± 2)	Day 36 (± 2)	Day 41 (±2)	Day 42 (± 2)	Day 43 (± 2)	Day 57 (± 3)
Informed Consent	X													
Medical History, demographics	X			X										
Physical Exam				X										
Vital Signs (blood pressure, heart rate, respiratory rate and temperature)				X	X	X	X	X	X	X			X	X
I/E Criteria	X			X										
Gravimetric Assessments ^{a, b}	X	X	X	X		X	X	X	X	X	X	X	X	X
HDSM-Ax, HDSS	X			X		X	X	X	X	X	X	X	X	X
DLQI				X									X	
Local Tolerability Assessments ^c					X	X	X	X	X	X			X	X
Adverse Events ^c		X	X	X	X	X	X	X	X	X	X	X	X	X
Randomization ^d				X										
Investigational Product ^e (IP) Dispensed / Returned					X ^f			X ^f					X	
IP Weight ^g					X			X					X	
Compliance Evaluation						X	X	X	X	X	X	X	X	
Safety Labs (hematology, chemistry, and urinalysis)	X												X	
UPT (females of childbearing potential only) ^h	X				X				X				X	
Concomitant Medication Review	X	X	X	X	X	X	X	X	X	X	X	X	X	X

- a) Gravimetric assessments for all visits will be conducted from **7:00am-11:00am**.
- b) One 5-minute gravimetric assessment will be conducted for each axilla.
- c) Investigator assessments to be performed after the Subject assessments.
- d) Randomization will take place only after the subject is qualified at the rescreening visit.
- e) Order the investigational product only after the subject is qualified at the rescreening visit and randomized.
- f) Pump 1 of 2 to be dispensed at Baseline (Visit 5). At Day 22 (Visit 8) Pump 2 of 2 to be primed and dispensed to patient. Written instructions for nightly dosing will be given to the subject. Subjects will apply their first dose of gel prior to bedtime the night of their Baseline visit. Instruct the subjects to return Pump 1 of 2 at Day 22 Visit 8 and Pump 2 of 2 at Day 43 (Visit 13, End of Treatment).
- g) Pump container 1 of 2 will be weighed after priming at Baseline prior to dispensing to the subject and upon return at Day 22 (Visit 8). Pump container 2 of 2 will be weighed after priming at Day 22 (Visit 8) prior to dispensing to the subject and upon return at Day 43 (Visit 13, End of Treatment).

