4. The proportion of subjects achieving at least a 50% reduction in gravimetrically measured sweat production (both axilla combined) from baseline to Days 8, 15, 22, 29, 36, 41, 42, 43, and 57.
5. Percent change from baseline in gravimetrically measured sweat production at Days 8, 15, 22, 29, 36, 41, 42, 43, and 57.
6. Absolute change from baseline in gravimetrically measured sweat production at Days 8, 15, 22, 29, 36, 41, 42, 43, and 57.
7. Ranked change from baseline in gravimetrically measured sweat production at Days 8, 15, 22, 29, 36, 41, 42, 43, and 57.
8. The proportion of subjects achieving at least a 1-point improvement in the HDSM-Ax score and at least 50% reduction in gravimetrically measured sweat production from baseline to Days 8, 15, 22, 29, 36, 41, 42, 43, and 57.
9. The proportion of subjects achieving at least a 2-point improvement in the HDSM-Ax total score and at least 50% reduction in gravimetrically measured sweat production from baseline to Days 8, 15, 22, 29, 36, 41, 42, 43, and 57.
10. The proportion of subjects achieving at least a 2-point improvement in HDSS from baseline to Days 8, 15, 22, 29, 36, 41, 42, 43, and 57.
11. The proportion of subjects achieving at least a 1-point improvement in the HDSS on Days 8, 15, 22, 29, 36, 41, 42, 43, and 57.
12. Change in the modified DLQI from baseline to Day 43 (end of therapy).

6.4.2 *Description of Safety Variables*

The following safety assessment measures will be conducted:

- Adverse events
- Local tolerability assessments including burning, itching, dryness, scaling and erythema
- Vital signs (blood pressure, pulse rate, respiratory rate, and temperature)
- Laboratory tests (hematology, chemistry, and urinalysis) and pregnancy testing in females of child bearing potential.

6.4.2.1 *Adverse Events*

An AE can be any unfavorable and unintended sign (including an abnormal laboratory finding, for example), symptom, or disease temporally associated with the use of a medicinal (investigational) product, whether or not considered related to the medicinal (investigational) product. This definition includes the worsening of a pre-existing condition, the development of investigational product dependency, and suspected investigational product-drug interactions.

6.4.2.2 *Local Tolerability Assessments*

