included in the model both without and with treatment*visit interaction terms. Subject will be analyzed as a random effect. Similarly, MMRMs will also be performed for the primary efficacy endpoint using HDSM-Ax dichotomized response data, and HDSM-Ax + GSP dichotomized response data. The models will be the same as the model for continuous data but the dependent variable of interest will be the response status with a logit link, using the SAS Proc GLIMMIX module. Both the heterogeneous CS (CSH) and TOEP (TOEPH) covariance structures will be considered and the structure with lower AIC will be used. The percentage of responders will also be summarized at each visit in the result table.

MMRM analysis as described above will also be performed for continuous GSP data (both Normal model and using rank transformed data) and binary GSP response (i.e. 50% reduction from baseline) data.

7.4.4.3 *Additional Sensitivity Analysis*

An additional sensitivity analysis will be performed as follows. For subjects missing all 3 end of therapy values, the data will be imputed by the last three available post-baseline (i.e., from Day 8 onward) assessment values. This analysis will be performed for both the continuous data analysis and the binary data analysis using the same ANCOVA models as described above.

7.4.5 *Secondary and Other Efficacy Endpoint Analysis Methods*

Baseline and End of Therapy values for HDSS and GSP are defined as follows.

HDSS:

- Baseline value = average of two screening values, i.e., Visit 1 and Visit 4
- End of Therapy value = average of Days 41, 42, and 43 measurements, i.e., Visit 11, Visit 12, and Visit 13, respectively.
- End of Therapy Imputed value = includes subjects missing all end of therapy values, where data is imputed by the last three available post-baseline visits.

Gravimetric Sweat Production (both axilla combined total):

- Baseline value = the median of GSP1, GSP2, and GSP3 measurements obtained on Visit 2, Visit 3, and Visit 4, respectively. The mean value of the same visits will also be used for analysis.
- End of Therapy value = the median of GSP4, GSP5, and GSP6 measurements obtained on Visit 11, Visit 12, and Visit 13, respectively. The mean value of the same visits will also be used for analysis.

- End of Therapy Imputed value = includes subjects missing all end of therapy values, where data is imputed by the last three available post-baseline visits.

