- Where data from a single axilla is missing, data will be imputed by using the median of the last 3 available values for that axilla.
- Analyses of continuous data will be performed using both Normal model and rank-transformed data.

DLQI:

The DLQI total score is calculated by summing answers to questions 1 through 10, including both parts of Question 7. All questions must be answered at the first DLQI assessment. Subsequent DLQI assessments with a single missing answer will be scored 0 for that question and totaled. Subjects with more than one missing question will have the instrument dropped for that visit.

The DLQI's change from baseline at 43 days (Visit 13) will be compared between each BBI-4000 active arm and the vehicle arm using an ANCOVA model adjusting for the baseline DLQI score.

With the exception of DLQI, analysis for secondary and other efficacy endpoints will generally be similar to the HDSM-Ax analysis described in Section [7.4.4.1](#) and Section [7.4.4.3](#). For GSP results analyzed as continuous measures, analyses assuming Normality for the data distribution (i.e., comparing means) will be performed using ANCOVA as described in Section [7.4.4](#). In addition, continuous gravimetric change scores will also be analyzed with rank transformed data using the t test for ANCOVA models. For both Normal model and non-parametric ANCOVA, treatment and baseline value will be the independent variables and continuous gravimetric change scores or rank scores (of change values) will be the dependent variable as appropriate.

All non-primary analyses will be based on available data without missing data imputation unless otherwise specified.

A table by treatment arm and visit summarizing the number of subjects with non-missing data will be also provided for HDSM-Ax, HDSS, and GSP. Subjects with non-missing data will be summarized for Visits 1 and 4, combined, Visit 1, Visit 4, and missing data at both Visit 1 and Visit 4. The number of subjects with non-missing data at each of Visits 6 through Visit 14 will be summarized, and subjects with complete data at Visits 11, 12, and 13, combined, any 2 of the three (Visit 11, 12, or 13), any one of the three, and subjects missing data at all of Visits 11 through 13 will be summarized.

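### The single-axilla sweat imputation in SAP 7.4.5 has no treatment-period limit, so it carries pre-treatment values into Days 8 and 15 and on-treatment values into Day 57

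*SAP*

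**What the plan says.** The rule is one bullet in the GSP part of SAP 7.4.5. When one side has no value, "data will be imputed by using the median of the last 3 available values for that axilla". It names no visits and does not limit which values may serve as donors.

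The schedule decides what those donors are.

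- GSP is measured at Visits 1 to 4 and then on Days 8, 15, 22, 29, 36, 41, 42, 43 and 57, with none at the Baseline visit (Protocol 7.1; SAP Table 2).
- The baseline value is "the median of GSP1, GSP2, and GSP3 measurements obtained on Visit 2, Visit 3, and Visit 4, respectively".
- Dosing starts after those visits: "Subjects will apply their first dose of gel prior to bedtime the night of their Baseline visit" (SAP Table 2, footnote f).
- It ends with the "last application the night before attending the end of-treatment evaluation (i.e., Day 43 visit") (Protocol 5.3), so Days 41 to 43 are all on treatment.
- Day 57 is the "2 Week Follow-up / End of Study" visit (Protocol 7.2.11).

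Single-visit totals feed named endpoints in SAP 6.4.1.3, among them "at least a 50% reduction in gravimetrically measured sweat production (both axilla combined) from baseline to Days 8, 15" and the later visits, and "Absolute change from baseline in gravimetrically measured sweat production at Days 8, 15, 22, 29, 36, 41, 42, 43, and 57". The ranked and percent changes and the HDSM-Ax plus GSP composites use the same days. Under SAP 7.4.4.2 and the table programming notes, the GSP and composite repeated-measures models (MMRM) use Days 8, 15, 22, 29, 36 and End of Therapy.

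SAP 7.4.4.3 limits a different imputation, for subjects missing all three end-of-therapy values, to assessments from Day 8 onward. The single-axilla rule has no matching limit.

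**The concern.** Filling a gap from earlier values is reasonable only if those values come from the same treatment state. Here the state changes between GSP3 and Day 8, and again between Day 43 and Day 57, and the rule reaches across both changes. Early in treatment it pulls the total back toward baseline and can turn a true 50% responder into a non-responder. At the follow-up visit it carries on-treatment dryness into an off-treatment measurement and so hides loss of effect. Table 14.2.3.3 will count single-axilla gaps by visit, but counting them does not correct the filled values.

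**Working it through.** The plan gives no figure to reproduce on this point, so the check is the donor sequence followed by an illustration.

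**Step 1: donors.** Taking the last three values as the three scheduled measurements before the gap:

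| Gap at | Donors | Pre-treatment | On treatment |
|---|---|---|---|
| Day 8 | GSP1, GSP2, GSP3 | 3 | 0 |
| Day 15 | GSP2, GSP3, Day 8 | 2 | 1 |
| Day 22 | GSP3, Day 8, Day 15 | 1 | 2 |
| Day 29 to Day 43 | three preceding visits | 0 | 3 |
| Day 57 | Days 41, 42, 43 | 0 | 3 |

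At Day 15, if the Day 8 value is below both GSP2 and GSP3, the median is the lower of those two screening values.

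**Step 2: size at Day 8.** Let s be the measured axilla's share of the baseline total and r the true reduction on both sides. Assume the fill equals that axilla's baseline. Then

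scored reduction = 1 − [(1 − r)s + (1 − s)] = r × s.

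With equal axillae (s = 0.5):

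- r = 0.50 gives 0.25
- r = 0.60 gives 0.30
- r = 0.80 gives 0.40

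The result depends on s. Inclusion criterion 2b (50 mg per side, 150 mg combined) allows a 50/100 mg subject:

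- 50 mg side missing: s = 100/150, and a fall of 0.50 ÷ (100/150) = 75% on the measured side reaches the 50% threshold.
- 100 mg side missing: s = 50/150, and even a completely dry measured side scores only 33%.

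**Step 3: Day 15.** Simulation with independent lognormal noise (an assumption; the documents give no within-subject variability). The first figure in each cell is how often the median of the three donors is a pre-treatment value. The second is the mean fill divided by the mean true value.

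| True reduction | CV 0.3 | CV 0.6 |
|---|---|---|
| 30% | 78%; 1.26 | 70%; 1.17 |
| 50% | 93%; 1.69 | 78%; 1.52 |
| 70% | 99.6%; 2.78 | 91%; 2.36 |

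**Step 4: Day 57.** Let q be the true reduction remaining at Day 57 and r the on-treatment reduction. Then

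scored reduction = s × q + (1 − s) × r, an overstatement of (1 − s)(r − q).

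With s = 0.5 and full return to baseline (q = 0), r = 0.60 is scored as 0.30. For r from 0.50 to 0.80 the scored value runs from 0.25 to 0.40.

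**Step 5: weight of one subject.** With 50 evaluable subjects per arm (SAP 7.6), one subject scored 30% instead of 60% moves the arm's mean percent reduction by 30/50 = 0.6 percentage points. It moves the 50% responder rate by 1/50 = 2 percentage points.

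**Step 6: would the limit in 7.4.4.3 be enough?** No. With donors from Day 8 onward only, Day 8 has no donor and Day 15 has one, which is sound. Day 57 would still draw on Days 41 to 43.

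**The case against.** Four points can be made for leaving the rule alone.

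First, scope. The bullet sits in a list introduced as defining baseline and end-of-therapy values, so it could be read as governing only those. By-visit analyses would then follow the general SAP position of no imputation unless specified. This ambiguity is real. Table 14.2.3.3 lists single-axilla gaps at every visit through Day 57, which favours the broad reading, but the table does not say those gaps are filled. The meaning of the last three values is also open. If it means the last three on record, a Day 8 gap would be filled from later visits, which is no better.

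Second, consequence. The exposed analyses are the other by-visit endpoints and models placed under sensitivity analysis. The Day 8 and Day 15 error works against the drug. This stands, and it limits the weight of the point.

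Third, a reader might infer more than the documents support:

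- That whole totals come from the wrong period. Only one side is filled; the other is measured.
- That no filled subject can reach 50% at Day 8 unless the measured side is completely dry. That holds only for equal axillae; the 50/100 mg case above disproves it in general.
- That Day 57 contaminates the MMRMs. It is not in them.
- That the primary result is at risk. HDSM-Ax does not use GSP.

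Fourth, using the other axilla is a judgement. The documents give no correlation between sides, each side is dosed separately, and missed applications are recorded by side (Listing 16.2.5.1). This is fair, and it is an assumption of the repair.

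**Conclusion.** The rule gives a wrong value when followed as written at Days 8, 15 and 57. At Day 8 the scored reduction is about the measured axilla's reduction times its share of baseline, which is half the true reduction when the sides are equal. At Day 15 the same holds approximately whenever Day 8 is below both screening values. At Day 57 part of the on-treatment effect is credited to an off-treatment visit.

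The reach is the by-visit GSP and composite endpoints at those three days, and the GSP and composite MMRMs through Days 8 and 15. End-of-therapy GSP is normally unaffected because Day 41 draws on Days 22, 29 and 36; this fails only if those earlier values are missing for that axilla.

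The sizes rest on the broad reading of the bullet, on a fill equal to baseline, and at Day 57 on full return to baseline. The number of subjects is unknown and probably small. The correction should be made because it is cheap.

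**What to change.** Replace the bullet in SAP 7.4.5 before unblinding with a rule that:

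- states that it applies at every GSP visit and never takes donors from across the start or end of treatment;
- imputes the missing axilla as the other axilla's value at the same visit, multiplied by the subject's ratio of the missing side's median to the other side's median over GSP1 to GSP3;
- where that ratio cannot be computed, sets the visit total to missing and leaves that subject-visit out of the by-visit GSP and composite responder analyses.

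The last item needs explicit wording. The notes to Tables 14.2.2.1 and 14.2.3.13 count subjects without a defined improvement as non-responders, so simply setting the total to missing would reproduce the Day 8 error.

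List the rule in SAP 7.7. Protocol 10.3 bases non-primary analyses on available data only, SAP section 4 undertakes to explain departures from the protocol, and 7.7 does not mention this one.

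The cost is a short extra derivation and edited table notes, with no new data. The downside is an assumption that the left/right ratio stays stable on treatment; it may be imprecise where screening values are low.

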7.4.6 Statistical/Analytical Issues

7.4.6.1 Adjustments for Covariates

The ANCOVA model and binary logistic regression model to compare treatment groups for the primary endpoint will include a covariate adjustment for the baseline value. Select secondary endpoints will be analyzed similarly.

7.4.6.2 Handling of Dropouts or Missing Data

Generally, no imputations will be performed on missing data; all analyses will be based on observed data unless otherwise specified.

7.4.6.3 Interim Analyses and Data Monitoring

There are no interim analyses planned, nor is there a plan to establish a data monitoring committee for this study.

7.4.6.4 Multicenter Studies

This is a multicenter study, with approximately 25 sites expected to participate. Data collected from all study centers will be pooled for data analysis. The effect of study center on the efficacy analysis results may be explored post-hoc, as needed.

7.4.6.5 Multiple Comparisons/Multiplicity

To limit the study-wide false positive rate to 0.10, a gate-keeping hierarchical testing algorithm will be employed to assess statistical significance regarding the primary analyses for the primary efficacy endpoint, i.e. ANCOVA analyses on change from baseline in HDSM-Ax score. The hierarchy is, the comparison between BBI-4000 15% group and vehicle group will be considered first, if the result is favorable with a 1-sided $p < 0.10$, then the comparison between BBI-4000 10% group and vehicle will be considered. Similarly, if the BBI-4000 10% group is favorable with a 1-sided $p < 0.10$, then comparison between BBI-4000 5% group and vehicle will be considered. The same gate keeping hierarchical testing algorithm will be employed for both the binary data analysis and the continuous measurement analysis.

The primary efficacy analysis will be performed on the mITT population; the PP population will be utilized for selected efficacy analyses. The PP population is described in Section [7.2](#).

7.4.6.6 *Active-Control Studies Intended to Show Equivalence*

This study does not include an active-control product and is not intended to demonstrate equivalence between any two drug products.

7.4.6.7 *Examination of Subgroups*

There are no planned analyses to assess efficacy results by subgroups.

7.5 **Safety Analysis**

Safety analysis will be carried out for the Safety Population, to include all subjects who receive at least one dose of study drug. Subjects who do not complete the study, for whatever reason, will have all available data up until the time of termination included in the analysis. For safety analysis presented by study visit, the baseline value will be defined as the last value reported prior to first study drug administration.

7.5.1 *Extent of Exposure*

Extent of exposure to study treatment will be summarized for the Safety Population by treatment group. The duration of exposure will be presented in days and calculated as the date of last dose of study drug minus the date of first dose of study drug, plus one. Duration of exposure will be summarized using descriptive statistics. Drug (pump) dispensation will be provided in a listing, to include total drug delivered per subject. Each pump will be primed, then weighed, prior to dispensing pumps to subjects. Each pump will be weighed upon return. Total drug delivered will be calculated as the total weight of all pumps dispensed minus the total weight of all returned pumps.

7.5.2 *Adverse Events*

Treatment-emergent adverse events (TEAEs) are defined as those adverse events (AEs) with onset after the first dose of study drug or existing events that worsened after the first dose during the study. Treatment-emergent AEs will be summarized by treatment group. Events reported with a partial onset date (e.g., month and year are reported but the day is missing) will be considered to be treatment-emergent if it cannot be confirmed that the event onset was prior to the first dose of study drug based on the available date entries.

Verbatim terms on case report forms will be mapped to preferred terms and system organ classes using MedDRA version 19.1.

Summaries that are displayed by system organ class and preferred terms will be ordered by descending incidence of system organ class in the combined BBI-4000 group and preferred term within each system organ class. Summaries displayed by preferred term only will be ordered by descending incidence of preferred term in the combined BBI-4000 group. Summaries of the following types will be presented:

- Overall summary of number of unique TEAEs and treatment-emergent serious adverse events (SAEs) and subject incidence of TEAEs meeting various criteria;
- Subject incidence of TEAEs by MedDRA system organ class and preferred term;
- Subject incidence of the most frequently-occurring TEAEs (i.e., TEAEs occurring in \geq 10% of the Safety Population) by MedDRA system organ class and preferred term;
- Subject incidence of TEAEs related to study drug by MedDRA system organ class and preferred term;
- Subject incidence of TEAEs by severity grade, MedDRA system organ class, and preferred term;
- Subject incidence of TEAEs related to Study Drug by severity, MedDRA system organ class and preferred term; and,
- Subject incidence of SAEs by MedDRA system organ class and preferred term
- Subject incidence of SAEs related to study drug by MedDRA preferred term.

At each level of summarization (e.g., any AE, system organ class, and preferred term), subjects experiencing more than one TEAE will be counted only once. In the summaries of TEAEs by severity grade, subjects will be counted once at the highest severity reported at each level of summarization, and by each level of severity; in the summary of TEAEs by relationship, subjects will be counted once at the closest relationship to study drug.

Adverse event data will be presented in data listings by subject, treatment group, and event. Serious AEs and AEs leading to discontinuation of the study drug will be presented in separate data listings.

